7 MEASUREMENTS AND EVALUATIONS

7.1 Efficacy Measurements

7.1.1 Liver Iron Concentration

The liver contains 70% or more of total body iron, (17) justifying the use of liver iron concentration (LIC) as a measure of body iron load. (18,19,20,21) In the absence of effective iron chelation therapy, transfusion-dependent patients experience a progressive increase in LIC. (22) Although liver iron concentrations may differ from the concentrations of iron in other organs, it has been reported that patients with LIC greater than 7 mg iron/g liver (dry weight; dw) are at increased risk of iron-induced toxicity such as cardiac disease, hepatic fibrosis, diabetes mellitus and death. (19,23,24) The current goal for chelation therapy in transfusion-dependent patients is to maintain an "optimal" body iron burden corresponding to hepatic storage concentrations of less than 7 mg/g dw. (19)

MRI scans for liver iron will be performed at Visit 1, Visit 5, and Visit 9 (or early termination), and will be transmitted to a central laboratory for interpretation and LIC calculation.

7.1.2 Cardiac MRI T2*

Myocardial MRI T2* can be used to monitor the myocardial iron load resulting from chronic transfusions, with low T2* levels reflecting a high cardiac iron concentration and high T2* values reflecting low cardiac iron. This technique has been calibrated with cardiac iron concentration in post mortem hearts. (25) Studies in non-iron-overloaded patients reveal that

none have a cardiac T2* <20 ms, a value that is now widely used clinically as the threshold for cardiac iron overload. (26) The ability of cardiac MRI T2* to identify patients at risk of iron-induced cardiac disease and premature death has been reported, (27) and its predictive value has been prospectively evaluated in 652 transfusion-dependent thalassemia patients from 21 UK centers who had cardiac MRI T2* assessment and who had their cardiac status followed over time. (27) The results of this study demonstrate that the lower the cardiac MRI T2* value, i.e., the higher the cardiac iron load, the higher is the risk of developing iron-induced cardiac failure within the subsequent 12 months.

MRI scans for the assessment of cardiac MRI T2* will be performed at Visit 1, Visit 5, and Visit 9 (or early termination), and will be transmitted to a central laboratory for interpretation.

7.1.3 Serum Ferritin

The most commonly used method for the assessment of body iron burden is the measurement of serum ferritin concentration. (28,29,30,31,32,33,34) Ferritin is the major storage protein for iron. It is present in low concentrations in the plasma and is a reflection of total body iron. In transfusion-dependent patients, due to continual transfusional iron input and the lack of a natural excretory pathway for excess iron, a progressive increase in serum ferritin concentration occurs in the absence of effective iron chelation therapy. Sequential measurement of serum ferritin concentration remains the most common method for assessment of body iron burden, and in clinical practice it is the standard for identifying trends in iron status within individuals and across populations. Serum ferritin is therefore a useful index of changes in iron load status. For decades, a serum ferritin level above 2,500 µg/L has been considered an important indicator of the relative risk of death. (23,24,35)

Serum ferritin will be assessed at the start of the extension study and quarterly thereafter.

7.2 Safety Measurements

7.2.1 Adverse Events and Serious Adverse Events

7.2.1.1 Definition of Adverse Events

An adverse event (AE) is any untoward medical occurrence in a patient who is administered a pharmaceutical or other therapeutic product in a clinical study, not necessarily having a causal relationship with the product. An AE can therefore be any unfavorable and unintended sign, symptom, or disease temporally associated with the use of a product, whether or not considered related to that product.

AEs include:

- Exacerbation of a pre-existing illness, including acute episodes/crisis of a chronic underlying condition
- An increase in frequency or intensity of a pre-existing episodic event or condition
- A condition detected or diagnosed after study treatment administration, even though it may have been present prior to the start of the study
- A continuous persistent disease or symptom present at baseline that worsens following the start of the study
- Accidents (e.g., involving a motor vehicle)
- Reasons for changes in concomitant medication (type of drug and/or dose)
- Medical, nursing, or pharmacy consultation
- Admission to hospital and surgical operations
- Abnormalities in laboratory findings (e.g., clinical chemistry, hematology, urinalysis),
 ECG, or other assessments (e.g., vital signs) that are not part of a larger medical
 condition already recorded as an AE and which are judged by the investigator to be
 clinically significant. The investigator should exercise medical and scientific judgment in
 deciding whether an abnormal laboratory finding or other abnormal assessment is
 clinically significant.

AEs do not include:

- A pre-existing disease or condition present or detected at the start of the study that does not worsen
- Hospital admissions or surgical procedures that had been planned prior to enrolment into the study
- The disease or disorder being studied, or a sign or symptom associated with that disease or disorder, unless it has worsened
- An overdose of either the study treatment or concurrent medication without any signs or symptoms

7.2.1.2 Monitoring and Documenting of Adverse Events

AEs and SAEs that are related to the underlying medical condition for which the patient enrolled in the clinical trial will be recorded separately from others.

Patients will be instructed to report any AEs to the investigator or a delegate. In addition, the investigator will solicit information about the occurrence of AEs through open-ended, non-leading verbal questions such as:

- How are you feeling / How does your child seem to be feeling?
- Have you/ has your child had any medical problems since the last visit?
- Have you / has your child taken any new medications, other than those provided in this study, since the last visit?

Based on the patient's response to these questions, the investigator or delegate should ask additional questions relevant to the specific complaint, such as:

- How severe is/was the symptom?
- How often did the symptom occur?
- How long did the symptom last?

The patient should also be questioned about any previously reported AEs that have not resolved.

The investigator will evaluate all AEs for their relationship to the investigational product (Section 7.2.1.3), intensity (Section 7.2.1.4), and seriousness (Section 7.2.1.5), and will document any measures taken to address the event. There should be an attempt to establish a diagnosis of the AE based on signs, symptoms, and/or other clinical information. Wherever possible, a diagnosis should be documented, rather than the individual signs/symptoms. All information is to be clearly recorded in the source documents.

If the dosage of study drug is reduced or treatment is discontinued as a result of an AE, the circumstances leading to such reduction or discontinuation must be clearly documented.

All AEs must be followed until resolution, the condition stabilizes, the event is otherwise explained, or the patient is lost to follow-up. The investigator is responsible for ensuring that follow-up includes any supplemental investigations that are needed to elucidate the nature and/or causality of the AE as completely as possible. This may include additional laboratory tests or investigations, histopathological examinations, or consultation with other health care professionals.

7.2.1.3 Assessment of Causality

The relationship of an AE to the study drug should be determined by the investigator after thorough consideration of all available facts, including associative connections (time or place), pharmacological explanations, previous knowledge of the drug, presence of characteristic clinical or pathological phenomena, exclusion of other causes, and/or absence of alternative explanations. The causal relationship of an adverse event to study drug will be assessed according to the following criteria (based on World Health Organization definitions):

• Not related: Temporal relationship to study drug administration is missing or

implausible, or there is no evident cause.

• Possibly related: Reasonable time sequence to administration of study drug, but

event could also be explained by concurrent disease or other drugs

or chemicals.

Probably related: Reasonable time sequence to administration of study drug, and

unlikely to be attributed to concurrent disease or other drugs or

chemicals, and follows a clinically reasonable response on

withdrawal (de-challenge). Re-challenge information is not required.

• Definitely related: Plausible time relationship to study drug administration, and cannot

be explained by concurrent disease or other drugs or chemicals. The

response to withdrawal of the drug (de-challenge) should be

clinically plausible. The event must be definitive pharmacologically or phenomenologically, using a satisfactory re-challenge procedure

if necessary.

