1.3 Potential Risks and Benefits

The safety profile of deferiprone in patients with thalassemia has been extensively characterized. Apart from chromaturia, which is due to iron excretion and is harmless, the most commonly reported adverse events seen in clinical trials have been nausea, vomiting, abdominal pain, increased alanine aminotransferase, arthralgia, and neutropenia. Comprehensive safety information is provided in the US full prescribing information (USPI) and the Investigator's Brochure.

The most significant serious adverse event (SAE) associated with deferiprone use is agranulocytosis, defined as a confirmed absolute neutrophil count less than 0.5×10^9 /L. In

pooled clinical trials, the incidence of agranulocytosis was approximately 2% of patients. The mechanism of deferiprone-associated agranulocytosis is unknown. Agranulocytosis and neutropenia usually resolve upon discontinuation of deferiprone, but there have been some post-marketing reports of agranulocytosis leading to death.

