7.2.1.6 Reporting of Serious Adverse Events

All SAEs occurring up to 30 days following completion of or discontinuation from the study must be reported to the sponsor, regardless of whether they are suspected of having a causal relationship with the study drug. Any SAEs for which the investigator does suspect a causal relationship must be reported to the sponsor regardless of the time elapsed since the last dose of the study drug.

Patients will be instructed to report SAEs to the investigator **within 24 hours**, by telephone. In turn, the investigator must report all SAEs to the sponsor **within 24 hours** of occurrence or notification by the patient, using the sponsor's SAE form. The sponsor will provide contact information for reporting SAEs. An assessment of causality must be provided at the time of the initial report. The investigator or delegate must then complete and submit a follow-up SAE form to the sponsor **within 5 calendar days**, and must submit further follow-up forms if additional relevant follow-up information becomes available.

The sponsor will submit reports of SAEs to the appropriate regulatory agencies, in line with local regulatory requirements and timelines.

Investigators must report all SAEs to their IRB/IEC as well as to the sponsor. If any SAE that is considered at least possibly related to the study medication and is unexpected occurs at one site, the sponsor will promptly inform all other sites of this, and all investigators must then report this event to their own IRBs/IECs, following the same timelines as above or following local IRB/IEC policy, whichever takes precedence.

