9 STATISTICAL ANALYSIS

9.1 Endpoints

9.1.1 Primary Endpoints

- Adverse events (AEs): Frequency, severity, time to onset, duration, and relatedness to study product
- Serious adverse events (SAEs): Frequency and relatedness to study product
- Number of discontinuations due to AEs

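### As worded, the *Not related* causality category takes in well-timed events with no identified cause, which pushes the count of related events down by an amount the documents cannot size

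*Protocol*

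**What the plan says.** Protocol section 7.2.1.3 grades the relation of each AE to study drug in four categories, after asking the investigator to weigh all available facts. Those facts include "exclusion of other causes, and/or absence of alternative explanations".

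- *Not related* has two limbs joined by *or*. The first concerns timing: "Temporal relationship to study drug administration is missing or" implausible. The second follows in the same line: "implausible, or there is no evident cause".
- *Possibly related* needs reasonable timing, but the "event could also be explained by concurrent disease or other drugs" or chemicals.
- *Probably related* needs reasonable timing, another cause being unlikely, and a reasonable response on "withdrawal (de-challenge). Re-challenge information is not required".
- *Definitely related* needs plausible timing, no other explanation, a plausible response to withdrawal, and an event that is definitive on pharmacological or phenomenological grounds.

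The grade is then used in several places. Protocol section 9.1.1 and SAP section 6.1.1 name relatedness in the primary endpoints; for AEs the protocol lists "Frequency, severity, time to onset, duration, and relatedness to study product". In SAP Tables 14.3.1.1 and 14.3.1.8, only the top three grades count as related. Protocol section 7.2.1.6 starts the cross-site alert with "If any SAE that is considered at least possibly related to the study medication and is unexpected occurs at one site". It also makes the reporting of an SAE beyond 30 days after completion or discontinuation depend on the investigator suspecting a causal link.

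**The concern.** The second limb of *Not related* points the wrong way. When an event follows dosing at a plausible interval and no disease or other medicine accounts for it, that absence should count toward the drug, or at least should not settle the matter against it. The section's own list of facts to weigh treats it that way, and its two highest grades depend on it.

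The primary objective is long-term safety, and relatedness is one of the things the primary endpoint measures. A site that follows the text literally would move some unexplained events from related to not related. The reactions most exposed are those not yet recognised as effects of deferiprone. For an unexpected SAE, the same coding could stop other sites from being told. For a late SAE, it could stop the report from reaching the sponsor.

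**Working it through.** No arithmetic applies, since no sample-size, power or error-rate figure depends on this scale. The check takes an event with plausible timing and tests it against each definition in Protocol section 7.2.1.3 as written.

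| Event with plausible timing | Not related | Possibly | Probably | Definitely |
|---|---|---|---|---|
| A. No cause identified, no de-challenge information | Met, by the second limb | Not met: needs a rival explanation | Not met: needs a response on withdrawal | Not met: refers to withdrawal response and needs a definitive event |
| B. No cause identified, improved on withdrawal | Met, by the second limb | Not met | Met | Met only if the event is also definitive |
| C. Rival explanation evident | Not met | Met | Not met unless the rival is unlikely | Not met |

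Row A is the gap: the only category whose words fit is *Not related*. Row B is an overlap: the same event satisfies two categories at opposite ends of the scale, and nothing says which prevails.

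**Does row A occur under this protocol?** It can, in three ways.

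1. The drug is continued. Section 7.2.1.8.1 keeps patients with mild neutropenia on treatment unless infection intervenes or the count has not recovered after 14 days. Section 4.5.3 leaves interruption for raised ALT to the investigator's judgment. These show only that de-challenge information can be absent by design.
2. The event is fatal.
3. The report is early. Section 7.2.1.6 requires a causality call with the initial SAE report, due within 24 hours, when the work-up may be incomplete.

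**Where does the grade go?**

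- Depends on it: the related-AE row of SAP Table 14.3.1.1, the adverse drug reaction Tables 14.3.1.4, 14.3.1.5 and 14.3.1.7, the causality Table 14.3.1.8, the cross-site alert, and the duty to report SAEs after 30 days.
- Does not depend on it: overall AE and SAE incidence, AE severity, AE discontinuations, and the onset and duration analyses in SAP section 6.3.4, which set no relatedness condition.

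**Can the size be worked out?** No. Neither document gives the share of AEs with no identified cause, the share of those lacking de-challenge information, or how often the company upgrades a call. Assuming a share and reporting the related count as falling by that share only restates the assumption. The tables also count patients, not events, so a patient with any other related AE stays in the related-AE row. For that row, the loss runs from zero (every affected patient has another related AE, or the company upgrades the call) to the number of patients whose only drug-related AEs are of this kind.

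**The case against.** The strongest reply is that the scale as a whole grades the link between event and drug. In that context the clause can be taken to mean that no causal link to the drug is evident. The opening sentence also tells investigators to consider prior knowledge of the drug and the lack of other explanations, which steers them away from the literal reading. Nothing in the documents shows that any site applied it literally. This stands as a reason to expect a modest effect. It does not repair the text: the clause says something else, and two sites can follow it in good faith and code the same event differently.

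The safeguards are also real:

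- All SAEs up to 30 days after completion or discontinuation go to the sponsor whatever the causality call, and all SAEs go to the site's own IRB or IEC (Protocol section 7.2.1.6).
- The alert rule does not say whose assessment counts, so the sponsor could act on its own view. The rule also covers only unexpected events.
- A data safety monitoring board oversees the study (Protocol section 8).
- SAP Tables 14.3.1.1 and 14.3.1.8 use the worse of the investigator and company calls.

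These narrow the exposure but do not close it. Neither document gives the company a separate scale, so if it uses section 7.2.1.3 it inherits the same clause.

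A reader might infer three stronger things that the documents do not support.

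- *That the scale is a clean inversion, ranking every unexplained event below every explained one.* Row B shows otherwise: an unexplained event that improves on withdrawal also qualifies as *Probably related*.
- *That every well-timed unexplained event meets both* Not related *and* Probably *or* Definitely. Those two grades also refer to the response to withdrawal, so row A does not meet them.
- *That agranulocytosis, neutropenia or ALT rises would be hidden.* Section 1.3 lists them as known reactions, so prior knowledge of the drug points to relatedness. The statement there that "The mechanism of deferiprone-associated agranulocytosis is unknown" concerns mechanism, and it calls the event deferiprone-associated in the same breath. Confirmed agranulocytosis also requires stopping treatment, so de-challenge information will usually exist.

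**Conclusion.** The point holds as a defect in the measuring rule. Followed as written, the second limb of *Not related* misclassifies a well-timed event with no identified cause. Without de-challenge information that is the only category the event fits; with a positive de-challenge it competes with *Probably* or *Definitely related*.

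The direction is toward fewer related AEs in a component of the primary endpoint and in the adverse drug reaction tables. Missed cross-site alerts for unexpected SAEs and missed reports of late SAEs are possible consequences, not demonstrated ones. The size cannot be derived, and any percentage would be an assumption.

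The conclusion assumes that at least some investigators read the clause literally and that the company does not correct all of those calls. It does not extend to overall AE or SAE incidence or to AE discontinuations, and it gives no ground for saying that known deferiprone toxicities would be lost.

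**What to change.** 1. In Protocol section 7.2.1.3, delete the second limb of *Not related*. Replace it with wording that does not overlap with *Possibly related*, for example: *or the event is clearly and fully explained by a cause other than study drug, so that a contribution of study drug is not reasonably possible*. The bar has to be that high. Asking only for another evident cause would draw in events that now belong under *Possibly related*, and in sickle cell disease a candidate disease explanation will often be available.
2. State that an event with a reasonable time sequence and no identified alternative cause is at least *Possibly related*, even when de-challenge information is missing.
3. Apply the same definition to the company assessment behind the SAP's worst-case rule. It would also help to say in section 7.2.1.6 whose assessment starts the cross-site alert.
4. Before database lock, query AEs coded *Not related* that began on deferiprone and have no alternative cause documented in the source or the eCRF. The SAP describes treatment in the past tense, so many codes may already be entered and this step probably matters most.

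The cost is a short text change, matching site guidance and some query work. The query may need source checks, because neither document describes an eCRF field for the alternative cause. The number of adverse drug reactions may rise slightly.

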7.2.1.4 Assessment of Intensity

Intensity refers to the degree of discomfort or impairment associated with an event. The intensity of AEs is to be reported on the CRF as mild, moderate, or severe, according to the definitions provided below. In addition, to maximize consistency in assessment, it is recommended that the National Cancer Institute (NCI) Common Terminology Criteria for Adverse Events (CTCAE) scale be used.

Intensity	Corresponding NCI CTCAE Grade
Mild: awareness of a sign or symptom but easily tolerated	1
Moderate : discomfort sufficient to cause interference with normal daily activities	2
Severe : resulting in inability to do work or perform normal daily activities	3–5

7.2.1.5 Serious Adverse Events

An SAE is an adverse event occurring at any dose that results in any of the following outcomes:

- Death
- A life-threatening adverse event
- Inpatient hospitalization or prolongation of existing hospitalization
- A persistent or significant disability or incapacity
- A congenital anomaly in the offspring of a patient who received the study treatment
- An important adverse event that does not result in death, is not life-threatening, and does not necessitate hospitalization but which in the investigator's judgment may jeopardize the patient and may necessitate medical or surgical intervention to prevent one of those outcomes. Examples include allergic bronchospasm requiring intensive treatment in an emergency room or at home, blood dyscrasias or convulsions that do not result in inpatient hospitalization, or the development of drug dependency or treatment-related substance abuse.

Clarifications:

- "Life-threatening" means that the patient was, in the view of the investigator, at immediate risk of death from the event as it occurred. This definition does not include an event that, had it occurred in a more severe form, might have caused death.
- Hospitalization for elective treatment of a pre-existing condition that did not worsen during the study is not considered an AE.
- Complications that occur during hospitalization are AEs. If a complication prolongs hospitalization, the event is considered an SAE.
- "Inpatient" hospitalization means the patient has been formally admitted to a hospital for medical reasons. This may or may not be overnight. It does not include presentation at a casualty or emergency room unless the event meets one of the other criteria for being an SAE.
- With regard to the criteria for an important adverse event, medical and scientific
 judgment should be used in deciding whether prompt reporting is appropriate in this
 situation.

